**Figure 2: Schematic of the quantitative and qualitative cohort in ANC and ART models**

For the secondary distribution cohorts, we will measure individual- and couple-level factors associated with acceptability to the index patient and intended user including: sex, age, previous HIV testing history, newly diagnosed or previously undisclosed HIV, relationship of the distributor and intended user (including type of relationship, age differential, measures of equality and empowerment), history of gender based violence and clinic from which the Index was recruited (ANC or HIV testing and treatment services).

The primary outcome of the secondary distribution cohorts is the:

- 1) Proportion of index patients who accepted an offer of secondary distribution HIVST kit(s) who report that their sexual partner(s) used the HIVST kit,

Secondary outcomes are the:

- 1) Proportion of index patients accepting an offer of HIVST kit(s) for secondary distribution,
- 2) Proportion of index patients who accepted an offer of a secondary distribution HIVST kit(s) who report that their partner used the HIVST kit(s) and linked to prevention or care services within 1-month of distribution

- 3) Proportion of intended recipients who self-report a) having used an HIVST kit and b) having attended confirmatory HIV testing, or HIV prevention or HIV care services within 3-months of distribution.

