### **7.3 Quantitative secondary distribution cohort data**

For the quantitative data arising from the secondary distribution cohorts, we will conduct analyses separately for the ANC and HIV testing and treatment cohorts. We will use descriptive analyses to describe the proportion of individuals accepting an offer of HIVST and the proportion who report that their partner used the HIVST. We will use standard logistic regression adjusting for study site to explore factors associated with accepting an offer of HIVST and with reported use of the HIVST.

Although the index individuals will be asked about linkage to care at 1-month follow-up, we will measure linkage to care using data from the intended users followed-up within 3-months after distribution. Linkage will be measured as the number of individuals reported to have linked to care (defined as accessing confirmatory testing services or attending an HIV care clinic for HIV-positive individuals or accessing VMMC services for HIV-negative males) among those who reported use of the HIVST.

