Known individuals who report serious incidents/ social harms including gender-based violence will be referred to the counsellor at the health facility. The lay counsellor will provide assistance and refer individual for further services or organisations if needed. Organisations where individuals who need additional services will be referred to are likely to include the community development officer, the gender-based violence unit at the local police post, Young women Christian Association (YWCA) and the Young Men Christian Association (YMCA) as well as any other identified organisations.

At the time of distribution, the primary HIVST distribution staff from MOH or SFH will ensure that women choosing to take a HIVST for their male partner will also be informed that counselling for the couple on their HIV test result or support (including reporting social harms)

in conducting the oral HIV self-test is available at the distribution points. Where a man at the HIV testing and treatment services or other distribution models is requesting a HIVST for his female partner to use, the lay counsellors will similarly assess whether there is likely any risk of coercion to test. The SFH, MOH or Zambart staff or lay counsellors will ensure that the person they offer the test kit understands the consequences of forced testing and acknowledges that they will not force anyone to test using the kit. In the training given to lay counsellors prior to the implementation of a 3ie-funded HIVST trial (LSHTM ethics ref 11846; UNZABREC ref: 003-09-16) nested within the HPTN 071 PopART trial (both conducted by Zambart), potential social harms and actions to be taken by the lay counsellors were discussed. In the training, the lay counsellors learnt to categorise incidents between serious and non-serious and between those related and those not related to the study. They also learnt how to report and what reporting template to use according to the category the incident falls in. Zambart will work with SFH and MOH to ensure that information from the 3ie- funded HIVST intervention applicable to this study is shared with all the staff and distributors involved in the distribution of HIVST kits. Zambart will also share information that will help in providing a refresher training that will include a discussion of social harms specific to distribution of HIVST.

Monitoring of social harms will be conducted by SFH/Zambart as described previously

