Link_HIV_Care 12	Do you have your ART/HIV care card number?	Record number preferably from card; Card not available; Did not agree	1; 2; 3
Section 7: For partners reporting an HIV negative test result			
Link_HIV_Care 13	After your unreactive HIV self-test, did you go to the clinic to access HIV-related services?	No: Yes	0; 1

Link_HIV_Care 14	What services did you access?		
Link_HIV_Care 15	After your HIV negative result, did you go for VMMC services?	No because I'm already circumcised; No, Yes	1; 2; 3 (if No or Yes, go to Link_HIV_Care 19)
Link_HIV_Care 16	At what age were you circumcised?	< 5 years of age; XX years	
Link_HIV_Care 17	When were you circumcised?	MM/YYYY	
Link_HIV_Care 18	What was the main reason why you were circumcised?	Tradition or religious; To protect myself against HIV; Hygiene; Other medical reason; Other (specify); Don't know	1; 2; 3; 4; 5; 6
Link_HIV_Care 19	After being referred, did you attend the VMMC clinic?	No Yes	1; 2
Link_HIV_Care 17	Why did you decide not to attend the VMMC clinic after being referred?	The clinic is too far; The hours of the clinic don't suit me; I did not have transport to go the clinic; I'm not interested in VMMC;	1; 2; 3; 4;
Link_HIV_Care 16	If yes, did you decide to get circumcised?	No, Yes,	0; 1
Link_HIV_Care 17	If yes, where was the circumcision done?	Health facility Home of a health worker/professional Circumcision done at home Ritual site	1; 2;

		Other home/place Don't know	
Finish	We have now come to the end of our questionnaire. Thank you very much for taking part in this study.		

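### Linkage in 7.3 is divided by all kit users, some of whom cannot meet its definition, so it is understated and does not show linkage among reactive users

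*Protocol*

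**What the plan says.** Protocol section 7.3 takes linkage from the intended users interviewed within three months of distribution. It is "defined as accessing confirmatory testing services or attending an HIV care clinic for HIV-positive individuals or accessing VMMC services for HIV-negative males". The sentence closes with the denominator: "accessing VMMC services for HIV-negative males) among those who reported use of the HIVST". The denominator is not restricted by result, sex or circumcision status. The same section states that "we will conduct analyses separately for the ANC and HIV testing and treatment cohorts", so the measure is pooled over test result but not over cohorts.

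The other statements on linkage differ:
- Section 4.3.2, secondary outcome 3, is worded as "Proportion of intended recipients who self-report a) having used an HIVST kit" and, as part b, attended confirmatory testing or any HIV prevention or care service. Objective 11 in 2.2 has the same breadth.
- Section 7.4 adds a description of linkage to ART or VMMC and of time to linkage, without a denominator. It names the index individual as the main source, where 7.3 names the intended user.

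The document foresees users who cannot meet the 7.3 definition:
- Section 10.2 covers the case where a man "is requesting a HIVST for his female partner to use".
- Item Link_HIV_Care 15 of the intended-user questionnaire (Appendix 3) offers the responses "No because I'm already circumcised; No, Yes".

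**The concern.** A proportion is interpretable when everyone in its denominator could have had the event. Under 7.3 two groups could not. An HIV-negative woman cannot access VMMC, and section 3 states that a non-reactive self-test needs no confirmatory test. An HIV-negative man who was circumcised before the kit arrived cannot newly access VMMC. Both count as not linked. So does a non-reactive woman who follows the advice in section 3 and returns to the facility for condoms.

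Section 5.4 says the linkage results are meant to describe pathways into care. There are two pathways here: reactive users towards confirmation and treatment, and non-reactive users towards prevention. One figure over both mixes them, and it moves with the sex and circumcision mix of the users as well as with their behaviour.

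**Working it through.** The protocol gives no expected linkage rate, so there is no figure of its own to reproduce. The check is algebra on the 7.3 definition.

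**Inputs.** All are assumptions, because the documents give none of these shares:
- p = share of users with a reactive result, 5-20%
- u = share of non-reactive users who are women or already circumcised, 20-60%
- Lpos = linkage among reactive users
- Lv = VMMC uptake among non-reactive men who could have it

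**Formulas.**
- 7.3 measure = p·Lpos + (1−p)(1−u)·Lv
- Share of users able to qualify = p + (1−p)(1−u)
- Eligible-only proportion = 7.3 measure ÷ share able to qualify

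The ratio of the 7.3 measure to the eligible-only proportion therefore equals the share able to qualify. It does not depend on Lpos or Lv, and it is below 1 whenever u is above 0 and some users are non-reactive.

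**Size of the understatement.**
- p = 5%, u = 60%: 0.05 + 0.95 × 0.40 = 0.43
- p = 10%, u = 40%: 0.10 + 0.90 × 0.60 = 0.64
- p = 20%, u = 20%: 0.20 + 0.80 × 0.80 = 0.84

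**Worked case**, p = 10%, u = 40%, Lpos = 80%, Lv = 10%:
- 7.3 measure: 0.10 × 0.80 + 0.54 × 0.10 = 13.4%
- Eligible-only: 13.4 ÷ 0.64 = 20.9%
- By result: 80% among reactive users, 10% among eligible non-reactive men

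**Can linkage among reactive users be recovered?** Keep p = 10% and u = 40%:

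| Lpos | Lv | 7.3 measure |
|---|---|---|
| 90% | 5% | 0.090 + 0.027 = 11.7% |
| 45% | 13.3% | 0.045 + 0.072 = 11.7% |
| 20% | 18% | 0.020 + 0.097 = 11.7% |

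Three very different results for reactive users give the same figure.

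**Numerator against 4.3.2.** Under outcome 3b a non-reactive woman or a circumcised man who attends any HIV prevention service counts as linked. Under 7.3 the same person does not. The structural failures therefore come from two features together: 7.3 names VMMC as the only prevention service, and it keeps all users in the denominator.

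**The case against.** Several points on the other side stand.

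- **Low stakes.** Section 5.4 calls linkage descriptive and not powered; the primary outcome is reported kit use. No test or sample size depends on this measure.
- **One cohort for women.** ANC kits go to male partners (Appendix 1), so the female-partner problem arises only in the HIV testing and treatment cohort. The cohorts are analysed separately, and 7.3 plans no comparison of linkage between them.
- **Result-specific data exist.** In the intended-user questionnaire, Section 6 is for reactive self-tests and Section 7 for negative ones, and 7.4 describes ART and VMMC linkage. A reader might infer that the plan hides linkage among reactive users. That goes too far: it can be tabulated. But no section commits to a reactive-only denominator.
- **Wording of confirmatory testing.** It could be read as open to anyone, which would let a non-reactive woman qualify. Section 3 makes that an unlikely route, and the form asks about confirmation only after a positive self-test.
- **The two denominators may be close.** Section 5.2 seeks contact only with partners whom the index reports as users, so most interviewed recipients should be users. The wording still differs.

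A reader might also infer that a collapse in care linkage would be lost in sampling error. That depends on the assumed reactive share. Take 100 interviewed users and a fall in Lpos from 80% to 20%. At 10% reactive the figure moves 0.10 × 60 = 6 points, within a half-width of about 7. At 20-40% reactive it moves 12-24 points, beyond a half-width of about 8-9. The claim is not general.

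Nor can structural non-events from different scenarios be added. An all-male group with 10% reactive and 30% of non-reactive men circumcised has 90 × 0.30 = 27 per 100. With 40% women and 20-40% reactive there are 24-32 women per 100 who cannot qualify. In that group circumcised men add only 0.60 × 0.60 × 30 = 11 to 0.60 × 0.80 × 30 = 14, so the total is about 35-46, not 51-59.

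**Conclusion.** The point holds as a defect in a stated definition, not as missing detail. Followed as written, 7.3 gives a proportion below that among users who could link, and linkage among reactive users cannot be derived from that proportion alone. The direction is certain once any HIV-negative woman or already-circumcised man has used a kit. The size is not: the factor of 0.43 to 0.84 rests on assumed shares (5-20% reactive, 20-60% of non-reactive users unable to qualify). The denominator is only part of the cause, because the 7.3 numerator is narrower than outcome 3b and objective 11. The consequence is limited to the interpretation of one descriptive secondary outcome, but the correction is cheap and should be made before analysis.

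**What to change.** In 7.3, replace the single measure by proportions reported by self-test result within each cohort:

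- (a) confirmatory testing, and separately HIV care, among users with a reactive result;
- (b) VMMC among non-reactive men not already circumcised, identified from the response "No because I'm already circumcised" at Link_HIV_Care 15 and the date-of-circumcision item;
- (c) any HIV prevention service among all non-reactive users, matching 4.3.2.

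Cite the later circumcision items by their wording: Link_HIV_Care 16 appears twice and 17 three times in that section of the form. Align outcome 3b in 4.3.2 and the linkage text in 7.4 with these denominators, and reconcile 7.3 and 7.4 on whether the intended user or the index is the main source.

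The change is to wording only, since the items are already collected. The cost is a smaller denominator and a wider interval for each proportion, most of all for (a). The form lets users withhold or not know their result; they fall outside (a) to (c), and their number should be reported.

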### **7.4 Cost data**

Cost data will be analysed separately by the economics team in STATA 14. Costs will be descriptively categorised into direct and indirect costs. To assess the economic burden HIVST,

we will compare sum of patients' direct non-medical and indirect costs with the household per capita expenditure. We will use a multivariable Tobit regression model to determine cost predictors.

Among individuals participating in the follow-up survey, we will describe reported use of the HIVST and investigate factors associated with reporting use of the secondary distribution HIVST. We will also describe linkage to ART or voluntary medical male circumcision, and time to linkage to care. Linkage data will primarily rely on reported use by the index individual, but we also aim to describe this among the intended users if consent is provided to follow-up partners and partners consent to participate in the study.

## **8 Ethical Considerations**

---

### **8.1 Consent**

Research staff from Zambart will be responsible for taking consent from individuals. Zambart train all staff in Good Clinical Practice and research ethics. For all research activities (except observations and mapping), individuals will need to provide written informed consent to participate. The researcher will first provide the potential participant with an explanation of the study as well as an information sheet with study details. This information will be provided in the language requested by the participant; English, Nyanja or Bemba. The researcher will explain that any individual-level data collected by the study may be shared publicly but will not contain the name or any personal identifier of the individual. The researcher will answer any questions raised by the individual and allow them sufficient time to come to a decision. Participants will then be required to give consent. Investigators request a waiver of parental/guardian consent for individuals aged 16 to 17 attending ANC and HIV testing and treatment services for the following reasons:

1. The cultural setting in Zambia is such that some women usually require permission from their husbands to consent for anything including HIV testing services. It will be particularly difficult for young women attending ANC and HIV testing and treatment services to freely decide whether to accept an HIVST kit for secondary distribution to their partner given the circumstances.
2. HIV self-testing is now standard practice in Zambia and individuals aged 16 and above can choose whether to self-test for HIV or not. The research component is not providing any additional testing or treatment, but rather exploring the experience of these individuals in using the HIVST. The research component is low risk and the probability and magnitude of possible harms that those aged 16-17 may encounter from this study is no greater than what they would encounter in standard HTS services.
3. Given their age, the potential participants may be involved in unfavorable power relationships with their parents or guardians.
4. Pregnant individuals aged 16-17 may not necessarily consider themselves minors. They will have probably made their own decision to come for ANC and those who have attended more than once will have received a lot of information strengthening their position as independent decision makers. All pregnant women are asked to give their own consent for

HIV testing and asked to bring their husband/partner for testing and so this is the normal situation in ANC.

5. Some participants attending HIV testing and treatment services especially HIV treatment may not have disclosed their HIV positive status (if HIV positive) to a third part. Therefore asking for parental/ guardian consent may lead to inadvertent disclosure

Given the reasons, the investigators recommend a waiver of parental consent and full written consent by all participants including those aged 16-17years attending ANC and HIV testing and treatment services.

In cases where participants are illiterate, they will be asked to provide a witness who is acceptable to them who will witness the entire information giving and consent process, give verbal consent plus a thumbprint certified by a witness.

Permission will be sought from MoH to access expenditure and resource utilisation records at health facilities to extract cost data.

Qualitative research activities will be facilitated by trained research assistants supported by the co-PI responsible for qualitative research of this study. Participants aged 16 to 17 will provide assent and consent will then be obtained from their parents or legal guardians. All interviews will be conducted in the language of the participant' choice and the IDI and FGD guides will be translated into two major languages commonly used in Lusaka; Icibemba and ci Nyanja. Participants will be asked for their preferred place of interview and day according to their availability for the interview as well as their perceived safety.

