## 5. Recruitment of study participants

---

All adults and adolescents aged 16 years or older (age of consent for HIV testing in Zambia) accessing HTS in clinics where HIVST distribution is being implemented are eligible for participation.

Specifically, individuals will be eligible to participate in data collection for the case studies if they:

- Are aged 16 years or older, and
- Able and willing to provide informed consent.

An individual is not eligible for participation in the study if they are:

- Under 16 years of age
- Unable and unwilling to provide informed consent
- Individuals not offered an HIVST kit, or
- If there is anything that, in the opinion of the investigator, would preclude informed consent or make study participation unsafe.

For the secondary distribution cohorts, participants are eligible if they meet these criteria and they are attending ANC or HIV testing and treatment services where secondary distribution of test kits is being offered. Informed consent will be sought for an exit interview and individuals who report accepting an offer of HIVST for secondary distribution to a partner will be eligible for a follow-up interview. Partners (intended users) of index individuals who collect an HIVST for secondary distribution will also be eligible for follow-up, providing consent is gained from the index individual at their follow-up interview and from the intended user.

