### 5.1 Recruitment of qualitative study participants

In total 46 IDIs, 12 FGDs, 4 stakeholder meetings and 15 observations will be conducted. The 42 IDIs will be conducted with purposefully selected individuals accessing VMMC (6), facility/ community-led (6), work places (6) ANC (12) HIV+ individuals (12) and health care workers (4). The 12 FGDs will be conducted with purposely selected community members to obtain community perspectives on the different models; 4 for the ANC model, 4 for HIV+ individuals' model, 1 for VMMC model, 2 for facility-led/community-led model and 1 for the workplace model. Of the 4 FGDs for the ANC model, 2 will be composed of individuals attending the ANC at the clinic and the other 2 of ordinary community members (women) recruited from the community. Similarly, the 4 FGDs for HIV+ will be divided into 2 (mixed sex) for individuals attending ART recruited from the clinic and the other 2 ordinary community members (mixed sex) recruited from the community. The VMMC and work place FGDs will be composed of individuals about to undergo VMMC and staff of work place. Stakeholder meetings will be conducted with representatives of different groups identified during community consultations. The four HCWs who are involved in distributing HIVST will be purposely selected (to ensure a

mix of gender and type or aspect of the model they are involved in) to take part in qualitative interviews. They will be asked for their perspectives on HIVST and the distribution models, linkage to care and prevention services, social harms and sustainability of the models. The study will be explained to them and consent obtained before taking part in the study. Other HCWs may take part in stakeholder meetings at the beginning of the study if the clinic/ HCWs are identified as key stakeholders in HIV care and prevention activities in the community.

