Twelve individuals (6 from the ANC and 6 from HIV+ individuals) recruited in the secondary distribution cohort will be purposively selected to participate in the qualitative cohort to explore the contextual factors affecting secondary distribution HIVST in ANC and through HIV-positive individuals. Individuals selected to participate in the cohort must have self-tested, and accepted secondary distribution on behalf of their partner. Using purposeful sampling, age, and gender will be taken into account to ensure a fair distribution of participants. Qualitative research assistants will spend extended times in the homes of the participants, using the rapport created to generate detailed data on participants' experiences with HIVST and particular the secondary distribution models. Such an ethnographic approach does not necessarily require many participants. RAs will inform quantitative cohort participants that they may be approached by researchers conducting qualitative research and asked to enrol in a qualitative cohort and that they will be asked to consent for this activity. Qualitative RAs will then approach the 12 individuals selected for the qualitative cohort and schedule interviews with them within 5 days. Follow-up interviews will be conducted immediately after the follow up visit for the quantitative cohort interviews. A key aspect of the qualitative cohort will be the extended contact with participants by the researchers in the participants' preferred milieu while at the same time conducting participatory research activities. The rapport created will be critical for prompting participants to share their experiences.

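### Section 8.1 gives two conflicting parental-consent rules for 16–17-year-olds recruited through ANC or HIV services into interviews and focus groups

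*Protocol*

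**What the plan says.** Section 5 opens the case studies to minors. Its first inclusion criterion reads "Are aged 16 years or older, and".

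Section 8.1 then sets two rules for those aged 16–17.

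- **Waiver.** "Investigators request a waiver of parental/guardian consent for individuals aged 16 to 17 attending ANC and HIV testing and treatment services". Five reasons follow. The fifth concerns patients of HIV testing and treatment services who may not have told anyone their status: "Therefore asking for parental/ guardian consent may lead to inadvertent disclosure". The section concludes: "the investigators recommend a waiver of parental consent and full written consent by all participants including those aged 16-17years attending ANC and HIV testing". That sentence names HIV treatment too.
- **Qualitative rule.** Further on, in the paragraph about qualitative activities: "Participants aged 16 to 17 will provide assent and consent will then be obtained from their parents or legal guardians". No setting is exempted.

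The qualitative participants come partly from the waiver's own settings. Section 5.2 says "Twelve individuals (6 from the ANC and 6 from HIV+ individuals) recruited in the secondary distribution cohort will be purposively selected" for the qualitative cohort. Section 5.1 describes two focus groups of women attending ANC and, for the HIV-positive model, "2 (mixed sex) for individuals attending ART recruited from the clinic".

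Table 3 asks for written consent for focus groups and in-depth interviews. It has no line for minors or for parents.

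**The concern.** A research assistant who has selected a 16-year-old ART client for an in-depth interview cannot tell from Section 8.1 whether to take the client's own written consent or to take assent and then approach a parent. Each course is prescribed by one paragraph and excluded by the other.

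What is at stake is participant protection. The protocol itself warns that contacting a parent may reveal the status of someone in HIV care, and such a disclosure cannot be undone. If staff follow the waiver instead, they depart from the written rule for qualitative work. If they avoid the problem by not selecting minors, the interviews and focus groups lose their youngest clinic patients without any decision having been made to exclude them.

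**Working it through.** No arithmetic applies. The check is whether one person can fall under both rules, and whether any text says which prevails.

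1. **Can a 16–17-year-old enter the qualitative work?** Yes. Section 5 sets the lower limit at 16 and makes no separate limit for interviews or focus groups.

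2. **How is the waiver bounded?** By setting: attendance at ANC or at HIV testing and treatment services. It is not bounded by method, and its conclusion speaks of all participants, including these minors.

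3. **Could the waiver be meant only for the exit interview and follow-up survey?** Nothing says so, and the reasons point the other way. The second reason describes the research as exploring how these individuals experience self-testing, and the Summary gives user experience (objective 2) to the qualitative component. The reasons about power relations with parents and about disclosure apply to an interview as much as to a questionnaire.

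4. **How is the qualitative rule bounded?** By method and age only. It covers 16–17-year-olds in qualitative activities wherever they were recruited.

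5. **Do the two sets overlap?** Yes, in two places:
   - The qualitative cohort is drawn from the ANC and HIV-positive quantitative cohorts (Section 5.2).
   - Two ANC focus groups and two ART focus groups consist of clinic attendees (Section 5.1), so 2 + 2 = 4 of the 12 planned focus groups.

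6. **Follow one person through.** A 16-year-old ART client accepts a kit for a partner and, under the waiver, consents alone to the exit interview. The client is then selected for the qualitative cohort: "Qualitative RAs will then approach the 12 individuals selected for the qualitative cohort", with interviews scheduled within five days. The waiver still applies because the client attends the service. The qualitative rule now applies as well, because the activity is an in-depth interview. One rule requires no parent and the other requires a parent.

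7. **Does any text settle it?** Table 3 does not, since its single word for interviews and focus groups fits either rule. Section 5.2 comes closest: it says cohort members will be told that they will be asked to consent to the qualitative activity, and it does not mention a parent. That leans towards the waiver but does not state an exception to Section 8.1.

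So the overlap is real, and no text in the review copy resolves it.

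**The case against.** The best defence is that the two paragraphs can be read together. Qualitative work also recruits VMMC clients, workplace staff, users of the facility- and community-led models, and ordinary community members. All are eligible from 16 and are outside the waiver. The parental-consent sentence has a full role for them, and the waiver would then be the specific exception for ANC and HIV-service patients. The wording in Section 5.2 on consent to the qualitative cohort fits this. The reading is plausible and may be what was intended, but no text states it, and staff at a clinic need it stated.

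A second defence is that Appendix 2, which holds the information sheets and consent forms, is not in the copy reviewed and might show who needs a parent's signature. That limits what can be said about the whole protocol. Even so, a form would leave two opposed sentences standing in the section that governs consent.

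Third, the qualitative rule puts assent first, so a minor could decline before any parent is approached. That lowers the risk of disclosure. It does not remove the contradiction, and it leaves the minor to choose between involving a parent and not taking part.

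Some stronger readings are tempting and should not be drawn:

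- A reader might infer that the qualitative rule will cause disclosure. The protocol says only that it may, and gives that reason for HIV testing and treatment attendees. For ANC attendees the reasons are mainly autonomy and power relations.
- A reader might take the size of the qualitative cohort or the focus groups as the number of minors exposed. Those are whole samples. No age distribution is given, and selection is purposive.
- A reader might infer that intended users aged 16–17 are caught in the same conflict. The waiver is worded for those attending the services, and for the partner survey Section 5.2 and Table 3 ask for the partner's own written consent, with no parent required. Whether more should be said about such partners is a separate question.
- A reader might infer that evidence on social harms depends on these interviews. The follow-up questionnaire in Appendix 3 also puts social-harm questions to index patients.

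**Conclusion.** The point holds as an internal contradiction in Section 8.1. For 16–17-year-olds recruited through ANC or HIV testing and treatment services into in-depth interviews or focus groups, the waiver paragraphs and the qualitative paragraph prescribe different consent, and neither gives way to the other. Following the qualitative sentence as written risks, for HIV-service attendees, the disclosure that the protocol itself names. Following the waiver breaches that sentence.

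The number of people affected is unknown and may be small, possibly nil. The conflict touches no outcome, sample size or analysis. It still needs settling because the possible harm to an individual is irreversible and the correction is slight.

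The conclusion rests on two conditions: that minors may be selected for the qualitative work, as Section 5 allows, and that the removed consent forms do not contain an exception. The protocol records the waiver as requested and recommended, not as granted. If the ethics committees refused it, the conflict would disappear, but the waiver text would then have to be withdrawn.

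**What to change.** Before any 16–17-year-old is recruited, agree with the ethics committees which rule governs ANC and HIV-service attendees of that age in interviews and focus groups, and write it once in Section 8.1. One wording that fits the protocol's own reasons for the waiver, and Section 5.2, would limit the parental-consent sentence to 16–17-year-olds recruited outside those services. If the committees prefer the other rule, the waiver paragraphs should say that they do not extend to qualitative work, and should address the disclosure risk they raise.

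Add a line for participants aged 16–17 to Table 3 and bring the consent forms into agreement. The choice between the rules belongs to the committees. The contradiction gives no ground for changing the eligible age.

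The cost is a short amendment: one clause, one table line and a check of the forms. No sample size or procedure elsewhere need change.
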